

Statistical Analysis Plan (SAP): We will apply 2 main forms of statistical analyses a) to report the pre-post changes in mean terms, and b) to report the results according with the inter-individual responses based on the technical error criteria, where according with the error calculated in the three previous measurements registered by the sample that was voluntary. Thus, for example, we will classify the subjects in responders and non-responders by the technical error of measurement, and additionally, we will classify the subjects according with a responder and non-responder clinical criteria, where we will classify as responders to all subjects who can be able of changing an initial adverse clinical altered profile for a healthy new classification. Thus, the specific statistical methods that we hope to apply for each analysis are; test of normality and homoscedasticity assumptions using Shapiro-Wilk and Levene's tests, the Student's t test for the identification of differences at baseline. An ANCOVA will be conducted (for potential confounders outcomes) in those altered baseline differences outcomes. We also hope to apply the repeated measures of two-way (group, time) to assess occurrence of an actual training effect [i.e., $p < 0.05$ for the interaction (group \times time) for the different study outcomes]. Among the specific statistical methods we hope to apply the Bonferroni post hoc test we hope to apply when we can be seen test differences among groups. Similarly, we hope to apply the Cohen's d test in order to detect effect size, using the threshold values of 0.20, 0.60, 1.2, and 2.0 for small, moderate, large, and very large effects, respectively [18], with 95% confidence intervals (CI). The alpha level was fixed at $P < 0.05$ for statistical significance.

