Additionally, exercise training in MetS patients was also associated with a significant reduction in high-sensitivity C reactive protein, and insulin resistance, but independent of weight loss [10], being this last effect (i.e., weight loss) a non-necessary aim into morbid obese patients. However, considering that the cardiorespiratory fitness (CRF) have been reported to be a strong predictor of overall health, exercise training may improve CRF in patients with MetS [11, 12], and thus we speculate that the CRF related outcomes such as the walking perform can be relevant for the health in obese patients at risk of MetS. Additionally, the resistance exercise training (RT, i.e., a particular exercise training modality consisting in stimulating muscles using external weights), may help to reduce health markers as systolic blood pressure (SBP) in obese patients with MetS risk factors [13]. In addition, supervised RT improved muscle strength and functional capacity in patients with obesity undergoing bariatric surgery [14]. However, although RT has been widely studied in obesity [15], there is little information in the morbid obesity. On the other hand, there is poor knowledge similarly, about the interindividual variability to exercise training in terms of responders and non-responders (NR). For example, as in reducing fat markers, we have shown that more baseline fat (overweight, obesity) have showed higher fat decreases and thus less NR, we speculate that morbid obese patients could decrease more both fat and MetS markers than other peers with less fat as those with obesity. Objectives: to determine the effects of a resistance training programme (RT) in preventing or attenuating metabolic syndrome (MetS) in patients with morbid obesity. A second aim was to report the prevalence of NR in terms of improvements in MetS markers and other co-variables considered. Design: An experimental, and non-randomized control clinical study. Methods: In an experimental clinical trial, obese and morbid obese patients will be invited for participating in a lifestyle study including resistant training during 20 weeks for preventing MetS in this cohort. Participants will be

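### The SAP plans no control contrast for the non-responder result, so the NR count can be reported but not read as response to training

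*Combined protocol and SAP*

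**What the plan says.** The title announces NR prevalence, and the Objectives state: "A second aim was to report the prevalence of NR in terms of improvements in MetS markers". The Design is "An experimental, and non-randomized control clinical study"; no section describes the control group further. Training lasts 20 weeks (Methods).

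The SAP sets out two analyses, one of mean pre-post change and one of inter-individual response. For the second, "we will classify the subjects in responders and non-responders by the technical error of measurement", with the error taken from three previous measurements in a volunteer sample. A clinical rule is added, which counts as "responders to all subjects who can be able of changing an initial adverse clinical altered profile for a healthy new classification". The multiple of the technical error is not given. Nor is the denominator of the clinical rule: all subjects, or only those abnormal at baseline.

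The SAP then lists the methods for each analysis. The one between-group test of training is a two-way (group, time) repeated-measures analysis, used "to assess occurrence of an actual training effect" on the study outcomes.

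Under Patients and Recruitment, subjects with adherence below 80% are removed from the statistical analyses.

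**The concern.** Both rules label a person from a single observed change. That change is the sum of any response to training, the error in the two readings, and whatever would have happened over 20 weeks anyway. Under the clinical rule, people selected for being abnormal at baseline also tend to drift back across the threshold.

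For mean effects, the SAP accepts that training is judged by a contrast between groups. It sets no such standard for the NR result. If the plan is followed as written, a finding in the title would be a count whose training component cannot be separated from the rest. It could show many responders when training did nothing, or many non-responders when everyone benefited equally.

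**Working it through.** **Step 1. Does any listed method supply the contrast?**

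| SAP method | What it addresses |
|---|---|
| Shapiro-Wilk, Levene | Model assumptions |
| Student's t test | Baseline differences in means |
| ANCOVA | Means, adjusted where baselines differ |
| Two-way (group, time) repeated measures | Mean change between groups |
| Bonferroni post hoc | Mean differences |
| Cohen's d with 95% CI | Standardised mean difference |

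Levene's test comes closest to a comparison of spread, but it appears only under "test of normality and homoscedasticity assumptions using Shapiro-Wilk" and is not tied to change scores or to NR. No method compares responder proportions, or the SD of change, between groups.

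**Step 2. TE rule (illustration).** The plan has no figure to reproduce: it states no sample size, TE, TE multiple or expected NR rate. Assumptions: one reading before and one after, normal errors, within-person SD over 20 weeks of k × TE, and a responder cut-off of m × TE. The SD of a change is then k√2 × TE.

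With no true change, P(labelled responder) = 1 − Φ(m / (k√2)).

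| | k = 1 (measurement error only) | k = 1.5 | k = 2 |
|---|---|---|---|
| m = 1 | 24.0% | 31.9% | 36.2% |
| m = 2 | 7.9% | 17.3% | 24.0% |
| m = 2.33 | 5.0% | 13.6% | 20.5% |

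Example: m = 1, k = 1 gives 1 − Φ(1/1.414) = 1 − Φ(0.707) = 0.240. The 2.33 row is the one-sided 5% cut-off for a difference score, 1.645 × √2. It holds 5% only if 20-week variation is no larger than TE.

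Now suppose every subject truly improves by the same 3 TE and m = 2. P(labelled NR) = Φ((2 − 3) / (k√2)) = 24.0%, 31.9% and 36.2% for k = 1, 1.5 and 2. Nobody differs in response, yet a quarter to a third are called non-responders.

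**Step 3. Clinical rule (illustration).** Assume baseline and final values are bivariate normal with the same mean and SD, correlation ρ and no effect. Let a proportion p be abnormal at baseline, with c = Φ⁻¹(1 − p). Then P(normal at end | abnormal at baseline) = 1 − P(Y₁ > c, Y₂ > c) / p.

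| Abnormal at baseline | ρ = 0.6 | ρ = 0.9 |
|---|---|---|
| 40% | 35.6% | 17.4% |
| 70% | 18.2% | 8.9% |
| 90% | 6.8% | 3.5% |
| 95% | 3.6% | 1.9% |

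**Step 4. Precision of a contrast.** The Newcombe interval is built from the Wilson limits (l, u) of each proportion. For an assumed 60% v 24% with 20 per group, the Wilson limits are 0.387 to 0.781 and 0.105 to 0.458.

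- Lower: 0.36 − √[(0.600 − 0.387)² + (0.458 − 0.240)²] = 0.055
- Upper: 0.36 + √[(0.781 − 0.600)² + (0.240 − 0.105)²] = 0.586

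The half-width is (0.586 − 0.055)/2, about 27 points. With 30 per group it is about 22 points. For the clinical rule, an assumed 50% v 25% with 10 abnormal subjects per group gives −0.155 to 0.563, a half-width of about 36 points.

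**The case against.** The best reply is that the aim is descriptive. It is worded as reporting prevalence, which a raw count does, and the SAP ties a training effect only to the group-by-time interaction. This stands. A reader might infer that the plan will use the NR count as evidence that training works; the documents do not say so.

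A reader might also take the background remark "more baseline fat (overweight, obesity) have showed higher fat decreases and thus less NR" as proof of such a use. It is not. It compares people with more and less baseline fat, recalls earlier work and leads into speculation. It does not compare trained with untrained subjects.

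Nor do the documents show that controls would be left unclassified. The SAP speaks of the subjects generally, so controls, if measured, are covered. What is missing is the contrast and its interval. But the control group is undefined, and since class II and class III obesity are both eligible, the factor group could even mean obesity class. The remedy must therefore be conditional.

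The TE rule does allow for some measurement error, and TE may include some day-to-day variation if the three measurements were on separate days. The interval between them is not stated, so coverage of 20-week variation cannot be assumed. TE does nothing about regression to the mean under the clinical rule.

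Finally, a control contrast is not a clean safeguard. Allocation is not randomised. If the 80% adherence rule bites only in the trained group, a selected group would be compared with an unselected one. This stands and shapes the fix.

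**Conclusion.** The point holds in a limited form. The NR count as planned meets the stated aim but cannot be read as response to training, because nothing sets it against what happens without training. The mean-effect analysis for the first aim keeps its own between-group test and is unaffected.

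The documents do not fix the size. With no true change, measurement error alone would label 24% (1 × TE) or 8% (2 × TE) as responders, and about 2% to 36% of those abnormal at baseline would normalise. These figures rest on assumed TE multiples, 40% to 95% abnormal at baseline, correlations of 0.6 to 0.9, normality and single readings. A reader might take them as estimates of contamination in this trial. They show only that it can be substantial, and for a marker abnormal in nearly everyone the clinical-rule figure is small. This is a cheap improvement.

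**What to change.** Add to the SAP:

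1. State what the factor group means. If it includes an untrained control measured at the same times, report responder and NR proportions by both rules in each group, with the training-minus-control difference and a 95% Newcombe interval.
2. For the clinical rule, use as denominator those abnormal at baseline on that marker.
3. Fix the TE cut-off in advance and base it on the error of a difference score (TE × √2 for one reading before and after). The cut-off does not replace the contrast.
4. Repeat the contrast with subjects below 80% adherence included where their final data exist, and describe it as supportive because allocation is non-randomised.
5. If there is no untrained control, label NR prevalence as descriptive only.

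Baseline-adjusted risk differences and a comparison of the SD of change are optional and exploratory. A two-sided 5% F test has power of only about 0.31 (20 per group) or 0.45 (30 per group) to detect a doubled variance.

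The cost is SAP wording and analysis; no new measurement is needed if controls are already measured at the same times. The drawback is the wide intervals shown in the working: about 27 points either way with 20 per group, 22 with 30, and 36 with 10 per group under the clinical rule. Confounding from non-random allocation remains.

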**Title: PREVENTING METABOLIC SYNDROME IN MORBID
OBESITY WITH RESISTANCE TRAINING: REPORTING NON-RESPONDER
PREVALENCE**

ID: RP08042019

DATE: April 11, 2019

Study Documents

Scientific background: The prevalence of metabolic syndrome (MetS) and cardiovascular disease is expected to rise along with the global obesity epidemic [1]. MetS is a cluster of clinical risk factors, including abdominal (visceral) obesity, hypertension, elevated serum triglycerides, low serum high-density lipoprotein (HDL) and hyperglycaemia [2]. Additionally, MetS is also associated with a pro-inflammatory state that leads to an altered physiological balance of adipokines, insulin resistance, endothelial dysfunction and a pro-atherogenic state [3], that increase the cardiovascular risk when population have more fat as the obesity state [4]. The morbid obesity is considered as a chronic disease highly-related with MetS development [5]. The MetS for example, significantly decreases the life expectancy of individuals with morbid obesity [4] and increases the disease burden and economic costs associated with healthcare [6]. In this sense, more recently, there was reported that body mass index (BMI) and fat distribution showed higher associations with inflammation, fat indices, and more prevalence of MetS in morbidly obese subjects [7], claiming for an early prevention of the MetS in the morbid obese state. Exercise training has proven to be effective in inducing a clinically significant weight loss and reducing cardiovascular risk [8]. Exercise have reported to be associated with increased muscle mass, decreased body fat, and improved metabolic profile (i.e., improved glucose control and lipid levels) [9].

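### The two-class technical-error rule has no class for changes indistinguishable from measurement error, so the reported non-responder prevalence depends partly on measurement error

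*Combined protocol and SAP*

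**What the plan says.** The SAP paragraph names two main forms of analysis. The first is mean pre-post change. The second is "to report the results according with the inter-individual responses based on the technical error criteria". For the second, "we will classify the subjects in responders and non-responders by the technical error of measurement". The TE comes from repeat measurements, "where according with the error calculated in the three previous measurements registered by the sample that was voluntary". The SAP does not state the cut-off as a multiple of TE, its direction, or whether it refers to one measurement or to a difference between two. It mentions no third class and no interval for the individual change.

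A clinical classification is added: "we will classify as responders to all subjects who can be able of changing an initial adverse clinical altered profile for a healthy new classification". It stands beside the TE rule and does not modify it.

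The count of these labels is a main result. The Objectives say: "A second aim was to report the prevalence of NR in terms of improvements in MetS markers and other co-variables considered". The title carries the same aim: "REPORTING NON-RESPONDER PREVALENCE".

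**The concern.** With only two labels, a patient who does not pass the TE cut-off has to be called a non-responder. A change inside measurement error is an inconclusive individual result. It is compatible with no response and also with a real improvement that two noisy measurements could not show. The rule sets no smallest relevant improvement and puts no bound on the individual's true change, so it cannot separate the two.

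The second aim is at stake. If training helped everyone by the same amount, the plan could still report a substantial share of non-responders and present measurement error as variation between patients. Two markers or two groups could differ in NR prevalence only because TE is larger relative to the mean change in one of them. Raising the multiplier, to avoid calling unchanged patients responders, makes missed improvement more frequent.

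**Working it through.** **No figure to reproduce.** The documents give no TE, multiplier, reliability, SD, expected change, sample size or NR prevalence. Every input below is an assumption, and the results are illustrations.

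**Model.** Errors are normal and independent between visits. A pre-post difference carries error SD √2 x TE. The cut-off is taken as an improvement of k x TE, with k = 1 or 2. In baseline SD units, TE = √(1 - reliability). For a patient whose true improvement is d,

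P(called NR) = Φ[(k x TE - d) / (√2 x TE)].

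**Case 1: every patient truly improves by d = 0.5 SD, so true NR is 0%.**

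| Reliability | TE | √2 x TE | Called NR, k = 1 | Called NR, k = 2 |
|---|---|---|---|---|
| 0.80 | 0.447 | 0.632 | Φ(-0.083) = 46.7% | Φ(0.624) = 73.4% |
| 0.90 | 0.316 | 0.447 | Φ(-0.411) = 34.1% | Φ(0.296) = 61.6% |
| 0.95 | 0.224 | 0.316 | Φ(-0.874) = 19.1% | Φ(-0.167) = 43.4% |
| 0.98 | 0.141 | 0.200 | Φ(-1.793) = 3.6% | Φ(-1.086) = 13.9% |

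Other assumed gains widen the range. At d = 1.2 SD and reliability 0.8-0.9, k = 1 gives 2-12%. At d = 0.2 SD and the same reliabilities, k = 2 gives 83-86%.

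**Case 2: responses vary normally, mean μ and SD s in TE units.** Now P(called NR) = Φ[(k - μ)/√(s² + 2)], and the true share with no improvement is Φ(-μ/s).

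- k = 1, μ = 1, s = 1: called 50%; true Φ(-1) = 15.9%.
- k = 1, μ = 2, s = 1: called Φ(-1/√3) = 28.2%; true Φ(-2) = 2.3%.
- k = 1, μ = 4, s = 1: called Φ(-3/√3) = 4.2%; true about 0%.

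The excess is large when the mean gain is 1-2 TE and small once it is well above that.

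**Case 3: two distinct groups, k = 1.** Suppose 60% gain 6 TE and 40% gain nothing. Called NR = 0.6 x Φ(-5/√2) + 0.4 x Φ(1/√2) = 0.6 x 0.000 + 0.4 x 0.760 = 30.4%, against a true 40%. The prevalence is understated because 24% of the unchanged patients are called responders.

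**Case 4: NR defined as a true change below the cut-off.** With k = 1, μ = 0.5, s = 1, called NR is Φ(0.5/√3) = 61.4%, against a true Φ(0.5) = 69.1%. This too is understated, although 69% of patients truly improve.

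**Check of a model-based correction.** One could subtract 2 x TE² from the variance of change and report the share of the fitted normal distribution at or below zero. In simulation (20,000 runs, n = 20 and 40, TE treated as known):

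| Truth | True NR | Rule, 1 x TE | Corrected estimate |
|---|---|---|---|
| All improve 0.5 SD (reliability 0.8-0.9) | 0% | 34-47% | 0.7-3.4% |
| Normal, mean 0.5 SD, SD 0.4 (reliability 0.8-0.9) | 10.6% | 38-47% | 10.4-11.0% |
| Nobody changes | 100% | 76% | about 50% |
| 60% gain 3-6 TE, 40% gain nothing | 40% | 30-35% | 11-12% |

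The correction works when true responses are normal with a positive mean. In the last two rows it does worse than the raw rule. When nobody changes, the estimated response variance is at or below zero in 53-55% of runs.

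**The case against.** The strongest reply is that the SAP does not state the rule criticised here. It gives no multiple and no direction, and it nowhere says that a change inside the error shows absence of response. That is correct: the improvement cut-off is an inference, though the natural one, and the numbers depend on it. What remains is that two labels with no third class force the inconclusive patients into one of them, whatever the multiple.

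A reader might also infer that NR prevalence must be overstated whenever most patients truly improve. Cases 3 and 4 show that this does not follow.

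The magnitude comes from chosen inputs. With very reliable measurements or large gains, the problem nearly disappears.

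The plan does not rest on TE counts alone. It adds the clinical criterion, and it judges a training effect by the group-by-time interaction. Neither repairs the TE count, but the analysis of the first aim is unaffected.

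Finally, it is tempting to say that the plan predicts a lower NR prevalence in morbid obesity and could not test it. The Scientific background does not say that. Its remark on fewer NR describes results already obtained in overweight and obesity, while its speculation concerns larger decreases: "we speculate that morbid obese patients could decrease more both fat and MetS markers than other peers".

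**Conclusion.** The concern holds in a limited form. The documents establish a two-class TE rule with no class for inconclusive changes, and its count serves the second aim and the title. The reported prevalence therefore mixes response with measurement error. Overstatement is likely under three conditions together: NR means no true improvement (the reading closest to the Objectives), responses are roughly normal, and the mean gain is positive but only a few TE. Outside these conditions the error can run the other way.

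The size cannot be derived from the documents. On the assumed inputs it runs from near zero to more than 70 percentage points. The model treats TE as covering all variation between visits. The retest interval is not given, and if the repeats were close together, variation over 20 weeks could be larger and misclassification worse.

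**What to change.** Change the SAP paragraph as follows.

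1. Set the cut-off on the error of a change score, √2 x TE, and state its multiple and, for each marker, the direction that counts as improvement.
2. Use three classes: improved beyond error, change not distinguishable from measurement error, and worsened beyond error. Report all three proportions with 95% CIs, and do not count the middle class as NR. Reword the second aim to match.
3. As a sensitivity analysis only, compare the SD of change between the training and control groups to judge whether true individual differences in response exist. The documents do not describe what the comparison group receives, so this requires that it be untrained; allocation is also not randomized. Label any error-corrected NR share as dependent on normal true responses. Label it as unreliable when the estimated response variance is near or below zero or when responses fall into distinct groups.

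To illustrate item 2, take a multiple of 1, reliability 0.9 and a uniform gain of 0.5 SD, so that 0.5/0.447 = 1.118. Then 1 - Φ(1 - 1.118) = 54.7% are labelled improved, Φ(-1 - 1.118) = 1.7% worsened, and the remaining 43.6% are reported as inconclusive.

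The cost is SAP wording and a short calculation from data already planned, with no new patients or measurements. The downside is that fewer subjects receive a definite label and the NR figure is less crisp.

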recruited from the morbid obesity (Temuco, Chile), during two months by phone invitation. The sample size will be determined in accordance with the study's feasibility recruitment, and a previous pilot study where it was determined the effects of a RT programme on anthropometric parameters, muscle function and metabolic profile and nutritional in the potential morbid obese patients [8]. The study will be completed in accordance with the Declaration of Helsinki and was approved by the Ethical Committee of the Universidad de La Frontera, Temuco, Chile. Patients and Recruitment: The inclusion criteria will be as follows: i) older than 18 and younger and =65 years of age (i.e., 65 y is the retirement age in women in Chile), ii) daily activities including walking, physical autonomy, iii) medical authorization by a physician, and iv) body mass index (BMI) =35 kg/m², according to BMI, general population is classified: class II obesity (BMI =35.0-39.9 kg/m²), class III - extreme obesity or morbid obesity (BMI =40 kg/m²) [16, 17]. Exclusion criteria will be: i) physical limitations (e.g., restricting injuries of the musculoskeletal system, or dependent of a third person), ii) exercise-related dyspnoea or respiratory alterations, iii) chronic heart disease with any worsening in the last month, and iv) an adherence rate of less than 80% of the total interventions (excluded from the statistical analyses).

REFERENCES

- [2] Alberti KG, Eckel RH, Grundy SM, Zimmet PZ, Cleeman JI, Donato KA, et al. Harmonizing the metabolic syndrome: a joint interim statement of the International Diabetes Federation Task Force on Epidemiology and Prevention; National Heart, Lung,

and Blood Institute; American Heart Association; World Heart Federation; International Atherosclerosis Society; and International Association for the Study of Obesity. *Circulation*. 2009;120:1640-5.

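### The planned two-way repeated-measures test uses only participants with both pre and post values, and its training effect can be biased if loss relates to baseline differently by group or the effect varies with baseline

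*Combined protocol and SAP*

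**What the plan says.** The SAP's first form of analysis is "to report the pre-post changes in mean terms". The training effect is to be judged from the group × time interaction: "We also hope to apply the repeated measures of two-way (group, time) to assess occurrence of an actual training effect". No visit between the pre and post measurements is described. Methods gives the duration: "lifestyle study including resistant training during 20 weeks for preventing MetS in this cohort". Design describes "An experimental, and non-randomized control clinical study".

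Baseline adjustment is conditional: "An ANCOVA will be conducted (for potential confounders outcomes) in those altered baseline differences outcomes". Patients and Recruitment lists, as an exclusion criterion, "an adherence rate of less than 80% of the total interventions (excluded from the statistical analyses").

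The document names no imputation, mixed model or other treatment of missing post values, and no analysis set of all enrolled participants. It gives no sample size, standard deviation or expected dropout rate.

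**The concern.** With two time points, a conventional repeated-measures analysis drops anyone who has only a baseline value, so the interaction is estimated in completers. Participants with worse starting values tend to move back towards the mean. If such participants are lost more from one group than from the other, that group's mean change shifts even when training does nothing. If the effect itself depends on baseline, equal losses in both groups also change the average effect being estimated.

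The background section makes this more than a formality: "we speculate that morbid obese patients could decrease more both fat and MetS markers than other peers with less fat". The investigators therefore expect change, and possibly the effect, to vary with baseline. Without randomisation, nothing in the design balances severity between the groups. At stake are the size of the interaction and, to a lesser extent, its significance.

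**Working it through.** **No planned figure to reproduce.** The document states no N, SD, effect size or dropout rate, so every number below except the design features is an assumption.

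**Step 1. What the test uses.** With two times, the group × time F equals the square of the two-sample t on change scores. In a simulated example with 20 per group, F = 14.405 and t² = 14.405. A participant without a post value has no change score and contributes nothing.

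**Step 2. When this biases the estimate.** Work in baseline SD units. Let λ be the slope of post on baseline in a group, and S the shift in that group's mean baseline caused by losing participants. If loss depends on baseline only, then

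bias = (λ_T − 1)·S_T − (λ_C − 1)·S_C

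where T is training and C is control. The bias is zero if S_T = S_C and the slopes are equal, or if both slopes are 1.

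A large-sample simulation (2,000,000 participants per scenario, about 25% loss, true effect −0.5 SD, log-odds of loss 1 per baseline SD) agrees:

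| Loss depends on baseline | Slope / effect | Completers bias (SD) |
|---|---|---|
| equally in both groups | 0.6, constant effect | 0.00 |
| training only | 1.0, constant effect | 0.00 |
| training only | 0.8, constant effect | +0.05 |
| training only | 0.6, constant effect | +0.09 |
| opposite directions | 0.6, constant effect | +0.18 |
| equally in both groups | 0.6, effect grows 0.2 SD per baseline SD | +0.05 |
| training only | 0.6, effect grows 0.2 SD per baseline SD | +0.14 |

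The largest value is 0.18/0.5 = 36% of the assumed effect.

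**Step 3. Size in a small trial.** Assume 30 per group, no true effect, pre-post correlation r, 10% loss in the better two thirds of trainees, and control loss of 5–10% unrelated to baseline. For a standard normal baseline, the worst third has mean 1.091 and the rest −0.545. With loss d in the worst third,

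S_T = [(1 − d)/3 × 1.091 + 0.6 × (−0.545)] / [(1 − d)/3 + 0.6], and bias = (r − 1)·S_T.

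- d = 0.5: overall loss 23%; S_T = (0.182 − 0.327)/0.767 = −0.190
- d = 0.7: overall loss 30%; S_T = (0.109 − 0.327)/0.700 = −0.312
- d = 0.3: overall loss 17%; S_T = (0.255 − 0.327)/0.833 = −0.087

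| r | d = 0.3 | d = 0.5 | d = 0.7 |
|---|---|---|---|
| 0.5 | 0.04 | 0.09 | 0.16 |
| 0.6 | 0.03 | 0.08 | 0.12 |
| 0.8 | 0.02 | 0.04 | 0.06 |

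Simulation agrees, at 0.04–0.16 SD for d = 0.5–0.7 and 0.02–0.05 for d = 0.3.

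**Step 4. Against the noise.** At r = 0.6 and d = 0.7, about 21 trainees and 28 controls remain. SE = √(2 × 0.4) × √(1/21 + 1/28) = 0.26 SD, so the bias is 0.12/0.26 = 0.48 SE. Over d = 0.5–0.7 and all three correlations, two-sided type I error is about 6–8%.

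The bias is positive, so training looks worse when higher values are worse. At r = 0.6 the chance of a false finding of benefit falls from 2.5% to 0.7–1.2%.

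**Step 5. The alternative.** In the Step 3 setting, a likelihood estimate that keeps baseline-only participants has bias of 0.01 SD or less, with essentially the same SE. In the Step 2 scenarios, the version with a separate post-on-baseline regression in each group has bias of about 0.00 throughout. If loss in the training group depends on the unobserved post value, neither method is unbiased: −0.07 SD for completers and −0.11 SD for the likelihood estimate, both exaggerating benefit.

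**The case against.** **The SAP does not state that incomplete cases are deleted.** True. Deletion is inferred from the conventional use of the named method. With no missing-data rule, though, nothing else would apply.

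**A reader might infer that any dependence of dropout on baseline severity biases the test, or that the test is valid only if dropout is unrelated to severity.** That is too strong. The table in Step 2 has two cases with such dependence and no bias.

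**A reader might also infer that the sickest trainees will leave a supervised programme while controls have nothing to leave, and that the interaction is the sole basis for conclusions.** The document supports none of this. It applies "supervised" only to a cited study, does not describe the control condition, says nothing about who will drop out, and also plans responder analyses.

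**The size is modest.** The bias stays below the SAP's own 0.20 threshold for a small effect even under heavy assumed loss, and it works against claiming benefit. This stands, and it limits the urgency.

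**ANCOVA is already planned.** Baseline-adjusted ANCOVA in completers has bias of about 0.00 when loss depends on baseline and the effect is constant. But the SAP reserves it for outcomes that differ at baseline, and it keeps a bias of 0.03–0.05 SD when the effect varies with baseline and no group × baseline term is fitted.

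**The adherence rule is the larger, written source of selection.** This also stands. It removes even participants who have a post value, so a new model alone would not bring them back. Equally, dropping the rule would not recover participants without a post value under the planned test. Both changes are needed.

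**Conclusion.** The point holds in conditional form. The planned interaction test is in effect a completers analysis, and the SAP has no method for missing post values. Bias is plausible, because the investigators expect change to vary with baseline and allocation is not randomised, but it is not automatic.

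Under the assumed heavy loss among the worst-off trainees it is about 0.04–0.16 SD, less than one standard error; with 30% loss in that third it is 0.02–0.05 SD. These figures rest on assumed dropout rates, 30 per group, correlations of 0.5–0.8 and the same baseline distribution in both groups. In these settings the direction hides benefit when higher values are worse; loss that depends on the unobserved outcome can act the other way. The change is worth making because the better method costs almost nothing, not because the planned test is shown to fail.

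**What to change.** 1. For each outcome, replace the repeated-measures test with a likelihood-based linear mixed model: group, time, group × time, unstructured within-person covariance, and baseline means free by group because allocation is not randomised. Include all enrolled participants, also those with baseline only. Report the interaction with its 95% CI as the main result.
2. Let the covariance differ by group, at least as a check. A common post-on-baseline slope left a bias of 0.02–0.04 SD when the effect grew by 0.2 SD per baseline SD.
3. Amend Patients and Recruitment at the same time, so that the 80% adherence set defines a secondary analysis. Otherwise the two sections conflict and the excluded participants stay out.
4. Keep the completers analysis as a sensitivity analysis, and add one for loss that depends on the unobserved outcome, which the mixed model does not correct.

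The cost is SAP and protocol wording, standard software and slightly more analysis work. With complete data the interaction estimate is unchanged.
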